### **4.2. Variable Definitions**

#### **4.2.1. Age**

Subject age will be calculated as the integer part of the number of years from date of birth to the date of signing the informed consent form, using the following formula:

$$\text{Age} = \text{integer part of } (\text{date of informed consent} - \text{date of birth} + 1) / 365.25$$

If date of birth is missing, then the age entered in the Demography section of the CRF will be used instead.

#### 4.2.2. Prior and Concomitant Medication

Prior medication is defined as any nonstudy drug started before the first dose of INCB024360 or MEDI4736.

Concomitant medication is defined as any nonstudy drug that is taken as follows:

- Started before the date of first administration of INCB024360 or MEDI4736 and is ongoing throughout the study or ends on/after the date of first study drug administration
- Started on/after the date of first administration of INCB024360 or MEDI4736 and is ongoing or ends during the course of study drug administration

**Note:** A prior medication could also be classified as "both prior and concomitant medication" if the end date is on or after first dose of INCB024360 or MEDI4736. In the listing, it will be indicated whether a medication is prior only, concomitant only, or both prior and concomitant medication.

The start/stop dates recorded in the CRF by the investigator and his or her research staff will be used to identify when a concomitant medication was taken during the study. Any missing start date must be queried for resolution. Unresolved missing start dates will be handled as follows:

- If the date is completely missing, the medication will be considered both prior and concomitant.
- If only the day is missing, and the last day of the month is before the first dose date on Day 1, then the concomitant medication will be considered as starting before Day 1, and the incomplete date will be imputed as the last day of the month.
- If only the day is missing, and the first day of the month is after the first dose date on Day 1, then the concomitant medication will be considered as starting after Day 1, and the incomplete date will be imputed as the first day of the month.
- If only the day is missing, and the month is equal to the month of the first dose date on Day 1, then the incomplete date will be imputed as the first day of the month.
- If both the month and day are missing, and the last day of the year is before the first dose date on Day 1, then the concomitant medication will be considered as starting before Day 1, and the incomplete date will be imputed as if it is the last day of the year. Otherwise, the incomplete date will be imputed as if it is the first day of the year.

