## **6.7. Prior and Concomitant Medication**

For subjects in the safety population, prior medications and concomitant medications will be coded using the WHO Drug Dictionary and summarized by WHO drug class and WHO drug term. In the data listing, each medication will be recorded as prior, concomitant, or both prior and concomitant. Results will be summarized as number and percentage of subjects with prior and concomitant medications by preferred term and WHO drug class.

Prior medication information will also be used to identify anticancer medication received by subjects before enrollment into the study. Prior anticancer medication data will be summarized and presented by treatment group as well as listed.

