### 8.2. Adverse Events

#### 8.2.1. Adverse Event Definitions

A treatment-emergent adverse event (TEAE) is any AE either reported for the first time or worsening of a pre-existing event after first dose of study drug. Analysis of AEs (as discussed below) will be limited to TEAEs, but data listings will include all AEs regardless of their timing to study drug administration.

Adverse Events will be tabulated by the MedDRA preferred term and system organ class. Severity of AEs will be described and graded using the National Cancer Institute Common Terminology Criteria for Adverse Events (CTCAE) v4.03. The CTCAE reporting guidelines and grading details are available on the Cancer Therapy Evaluation Program website.

A grading (severity) scale is provided for each AE term. If the toxicity is not included in the CTCAE v4.03 criteria, it will be rated on a scale of 1 to 4 as follows: 1 = mild, 2 = moderate, 3 = severe, and 4 = life threatening. All toxicities will be graded based on the worst level reached, not the level they may have reached if they had not been treated. When the intensity of

an AE changes over time for a reporting period (eg, between visits), each change in intensity will be reported as an AE until the event resolves.

The subset of AEs considered by the investigator to be related to INCB024360 or MEDI4736 will be considered to be treatment-related AEs. If the investigator does not specify the relationship of the AE to study drug, the AE will be considered to be treatment related. The incidence of AEs and treatment-related AEs will be tabulated. Serious adverse events (SAEs) will also be tabulated.

Any missing onset date, causality, or severity must be queried for resolution. Unsolved missing values will be handled according to the following rules:

- An unsolved missing causality will be considered treatment related.
- An unsolved missing severity will be identified as an unknown severity.

For purposes of analysis, all AEs will be considered TEAEs unless the AE can unequivocally be defined as not treatment emergent. Therefore, an unsolved missing onset date will be considered treatment emergent, with the following exceptions:

- If the stop/resolution date is before the first dose administration date on Day 1, then the AE will be considered as not being treatment emergent.

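### SAP 4.2.2, read literally, counts a medication with a completely missing start date as concomitant even when its recorded stop date is before the first dose

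*SAP*

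**What the plan says.** SAP 4.2.2 defines a prior medication as a non-study drug begun before the first dose of either study drug. A drug begun before the first dose is also concomitant if it "is ongoing throughout the study or ends on/after the date of first study drug administration". The Note repeats the test: a prior medication can carry both labels "if the end date is on or after first dose of INCB024360 or MEDI4736".

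The section then turns to incomplete data. "Any missing start date must be queried for resolution", and five bullets cover start dates that stay unresolved. The first reads: "If the date is completely missing, the medication will be considered both prior and concomitant". It places no condition on the stop date.

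SAP 8.2.1 handles the parallel problem for adverse events. An event with an unresolved missing onset date is treatment emergent by default, subject to exceptions. One is: "If the stop/resolution date is before the first dose administration date on Day 1, then the AE will be considered as not being treatment emergent".

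The classification feeds the summaries in SAP 6.7: "Results will be summarized as number and percentage of subjects with prior and concomitant medications by preferred term and WHO drug class". The planned outputs are Tables 1.4.2.1 and 1.4.2.2 and Listing 16.2.3.3. SAP 4.2.2 says the listing will show whether each drug is prior only, concomitant only or both.

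**The concern.** A drug known to have stopped before Day 1 was not taken during study treatment, whatever its start date. The bullet nevertheless gives it the concomitant label. The missing start date is allowed to override a recorded stop date that already settles the question.

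At stake is the accuracy of the concomitant medication tables and of the listing flag. Any error runs in one direction, towards apparent on-treatment use. Two programmers working from the same section could also produce different tables, because it does not say whether the definition or the bullet takes precedence.

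**Working it through.** The documents state no figure here, so the check is one of logic. The rules are applied to records whose start date is completely missing after query.

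| Recorded stop | Definition and Note (SAP 4.2.2) | Missing-start bullet (SAP 4.2.2) | Agree? |
|---|---|---|---|
| Day -15 | Prior only | Both | No |
| Day 20 | Concomitant; prior status unknown | Both | Yes, as a default |
| Ongoing | Concomitant; prior status unknown | Both | Yes, as a default |
| Missing | Cannot be determined | Both | Yes, as a default |

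**The first row.** A drug that ended on Day -15 must have begun on or before that day, so it is prior. It is not ongoing and did not end on or after the first dose, so it fails the test for concomitant. The prior half of the bullet's label is right and the concomitant half is wrong.

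**Comparison with the other bullets.** Suppose only the start year is known, that it is the calendar year of Day 1, and that the drug stopped earlier in that year than Day 1. The last bullet imputes the start as the first day of the year, which is before Day 1. The definition can then be applied to the stop date and gives prior only. If the year is lost as well, the same stop date gives both. The other four bullets place or impute a start date and leave the class to the definition. Only the completely-missing bullet assigns the class itself.

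**Comparison with adverse events.** An event with a missing onset and a resolution on Day -15 is not treatment emergent under SAP 8.2.1. A medication with the same pattern of dates is concomitant under SAP 4.2.2.

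**Can such records exist?** Yes. Protocol 5.10 has the CRF record medication received up to 28 days before enrollment, so drugs stopped before Day 1 will be in the database. The bullet reaches them only if the start date is still wholly missing after query.

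**Size per record.** SAP 6.7 reports the number and percentage of subjects. One subject wrongly counted moves a percentage by 1/N. With the Protocol's planned cohort sizes:

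- Phase 2 melanoma, both stages: 1/40 = 2.5 percentage points.
- Phase 2 NSCLC at 300 mg BID: 1/28 = 3.6 percentage points.
- Phase 1 cohort of 6: 1/6 = 16.7 percentage points.
- Phase 1 cohort of 3: 1/3 = 33.3 percentage points.

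The count moves only if the subject has no genuine concomitant record under the same term or class. The documents do not allow an estimate of how many subjects would be affected.

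**The case against.** The strongest defence is that the section already handles the case if read as a whole. The definitions come first. The text then says "The start/stop dates recorded in the CRF by the investigator and his or her research staff will be used" to establish when a concomitant medication was taken, and several of the later bullets speak of placing a concomitant medication before or after Day 1. On that reading the bullets only locate the start of a drug already shown to be concomitant by its stop date, and a drug stopped before Day 1 never reaches them. Part of this stands: a careful programmer could work that way and avoid the error. But the section does not state that order. The bullet at issue refers to medications generally and assigns the final class directly, so the defence has to be supplied by the reader.

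A second defence is that counting a drug as possible exposure is the conservative choice when timing is unknown. That is fair when the stop date is also unknown. It does not cover a known stop date, and the SAP's equally conservative adverse event rule gives way in exactly that situation.

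A reader might infer two stronger points that the documents do not support.

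- **That the affected drugs are those stopped within the 14- to 21-day washouts.** Use inside those windows would generally exclude the subject under Protocol 3.3, criteria 5, 6 and 16. The bullet covers any non-study drug, and nothing suggests that missing start dates cluster in restricted classes. Prior anticancer medication also has its own tables (1.4.3.1 and 1.4.3.2) and a systemic cancer medication history listing (16.2.1.5).
- **That such records would appear as prohibited therapy on study.** Deviations are recorded by monitors in the Protocol Deviation Log (Protocol 11.2) and listed from it (SAP 6.3). They are not derived from the concomitant tables. Systemic steroids can also be used on study with medical monitor approval (Protocol 5.10.1 and 5.10.2), so a steroid row does not itself indicate a violation.

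**Conclusion.** The point holds as a minor inconsistency. On its literal wording, the completely-missing bullet contradicts the definition and Note in its own section for one pattern of data: start unknown, stop recorded before the first dose. It also departs from the SAP's adverse event rule. Records of any drug class with that pattern would be wrongly counted in the concomitant tables and wrongly flagged in the listing.

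The number is unknown and probably small, since it is limited to records whose start date is still missing after query. The tables are descriptive. Response rate, duration of response, PFS, dose-limiting toxicity and adverse event analyses do not use this classification, and sample size and error rates are untouched. The one possible further use is as a covariate in the population PK analysis, which SAP 7.5.2 and 7.5.3 make optional.

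This conclusion assumes the bullet is programmed as written. If the definition is applied first, the error does not arise, but the SAP does not require that order.

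**What to change.** Replace the bullet with: *If the start date is completely missing and the stop date is before the first dose, the medication is prior only; if the stop date is on or after the first dose, ongoing or missing, it is both prior and concomitant.*

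SAP 4.2.2 gives no rule for partial stop dates. It would help to add that a partial stop date counts as before the first dose only when its latest possible day is before Day 1, and is otherwise treated as missing.

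The change brings the bullet into line with the Note and with SAP 8.2.1, and keeps the conservative default where the stop date is unknown. It costs one or two SAP sentences and one extra condition in the program. No data collection or other analysis changes.

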## 5. STATISTICAL METHODOLOGY

### 5.1. General Methodology

Unless otherwise noted, SAS® software (SAS Institute Inc, Cary, NC; version 9.1 or later) will be used for the generation of all tables, graphs, and statistical analyses. Descriptive summaries for continuous variables will include, but not be limited to, the number of observations, mean, standard deviation, median, minimum, and maximum. Descriptive summaries for categorical variables will include the number and percentage of subjects in each category.

For the dose-escalation portion of the study, the Phase 1 safety population (defined in [Section 5.3.2](#)) will be used for all safety analyses, and the Phase 1 intent-to-treat (ITT) population will be used for all efficacy analyses. For the expansion portion of the study, the Phase 2 safety population will be used for all safety analyses, and the Phase 2 ITT population will be used for all efficacy analyses. Analyses of PK endpoints are described in [Section 7.5](#) and will be performed by the Incyte and MedImmune pharmacokineticist, respectively.

Interim safety analyses are planned for this study as defined in [Section 9](#).

### 5.2. Treatment Groups

Subjects will be summarized overall and based on the dose regimen initially assigned:

- 3 mg/kg IV MEDI4736 once every 14 days + 25 mg BID INCB024360 (Phase 1)
- 10 mg/kg IV MEDI4736 once every 14 days + 25 mg BID INCB024360 (Phase 1)
- 10 mg/kg IV MEDI4736 once every 14 days + 50 mg BID INCB024360 (Phase 1)
- 10mg/kg IV MEDI4736 once every 14 days + 75 mg BID INCB024360 (Phase 1)
- 10 mg/kg IV MEDI4736 once every 14 days + 100 mg BID INCB024360 (Phase 1)
- 10 mg/kg IV MEDI4736 once every 14 days + 200 mg BID INCB024360 (Phase 1)
- 10 mg/kg IV MEDI4736 once every 14 days + 300 mg BID INCB024360 (Phase 1)
- 3 mg/kg or 10 mg/kg IV MEDI4736 once Every 14 Days + selected MTD/PAD of INCB024360 (Phase 2: Melanoma)
- 3 mg/kg or 10 mg/kg IV MEDI4736 once every 14 days + selected MTD/PAD of INCB024360 (Phase 2: NSCLC)
- 3 mg/kg or 10 mg/kg IV MEDI4736 once every 14 days + selected MTD/PAD of INCB024360 (Phase 2: Pancreatic Cancer)
- 3 mg/kg or 10 mg/kg IV MEDI4736 once every 14 days + selected MTD/PAD of INCB024360 (Phase 2: SCCHN)

Table summaries, unless otherwise indicated, will be provided by treatment group. Note that separate summaries will be provided for the Phase 1 and Phase 2 portions of the study.

### **5.3. Analysis Populations**

#### **5.3.1. Phase 1 Intent-to-Treat Population**

The Phase 1 ITT population will include all subjects who are enrolled in the Phase 1 portion of the study. Treatment groups for this population will be defined according to the treatment assignment at the time of enrollment on Day 1 regardless of the actual study drug the subject might receive during his/her continued participation in the study. This population will be used for analyses of all efficacy data for Phase 1.

#### **5.3.2. Phase 1 Safety Population**

The Phase 1 safety population includes all subjects enrolled in the Phase 1 portion of the study who received at least 1 dose of INCB024360 or MEDI4736. Treatment groups for this population will be determined according to the actual treatment the subject received on Day 1 regardless of the actual study drug the subject might receive during his/her continued participation in the study. All Phase 1 safety analyses will be conducted using the Phase 1 safety population.

#### **5.3.3. Phase 2 ITT Population**

The Phase 2 ITT population will include all subjects who are enrolled in the Phase 2 portion of the study. Treatment groups for this population will be defined according to the tumor type at the time of enrollment on Day 1. This population will be used for analyses of all efficacy data for Phase 2.

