Approximately 140 to 192 subjects with advanced melanoma, NSCLC, SCCHN, TNBC, gastric or GE junction cancer, and TCC of the GU tract will be enrolled at the MTD or PAD of epacadostat in combination with durvalumab. More than 1 PAD may be evaluated in Phase 2. The approximate number of subjects needed for the melanoma, TNBC, and gastric and GE junction cancer cohorts will be determined using the Simon 2-stage design: Stage 1 will be the initial number of subjects per tumor type, and the decision to proceed with Stage 2 will be determined by the response rate observed in Stage 1 (further number of subjects to be enrolled in each stage per tumor type is detailed in Table 5). If more than 1 PAD is evaluated, the cohort may or may not be repeated for the specified tumor type as indicated in Table 5. The sponsor may limit enrollment of a specific tumor type to Stage 1.

Table 5: Approximate Number of Subjects by Tumor Type and Stage of Study

Tumor Type	No. of Subjects Enrolled		
	Stage 1	Stage 2 (If Study Proceeds to Stage 2)	Total (Stage 1 + 2)
Melanoma	15	25	40
TNBC	13	16	29
Gastric and GE junction cancer	9	11	20

Under Amendment 6, enrollment of the NSCLC, SCCHN, and TCC of the GU tract cohorts will be completed as expansion cohorts at the 300 mg BID dose level. The sample size for each cohort will be increased to account for the heterogeneity of PD-1 pathway–treated and PD-1 pathway–naïve subjects within the selected tumor types. The approximate number of subjects per tumor type is listed in Table 6, and the number of PD-1 pathway–treated subjects in each cohort will be limited to 10 in order to reduce the risk of any cohort having a significant imbalance between PD-1 pathway–treated and PD-1 pathway–naïve subjects, thereby preserving the predicted levels of baseline efficacy observed with PD-1 pathway monotherapy. Subjects enrolled at the 100 mg BID dose level will be analyzed independently.

Table 6: Approximate Number of Subjects for Expansion Cohorts

Tumor Type	No. of Subjects Enrolled	
	100 mg BID ^a (n = 19)	300 mg BID ^b (n = 84)
NSCLC	8	28
SCCHN	7	28
TCC of the GU tract	4	28

^a Subjects enrolled in the 100 mg BID dose level were enrolled before Amendment 5.

^b All subjects in the 300 mg BID NSCLC, SCCHN, and TCC of the GU tract cohorts enrolled in Amendment 5 or earlier are included in the total sample size.

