Table 33: Details of Simon 2-Stage Design (Melanoma, TNBC, and Gastric and Gastroesophageal Junction Cancer)

	Melanoma ($P_0 = 30\%$, Target RR = 55%)	TNBC ($P_0 = 15\%$, Target RR = 40%)	Gastric and GE Junction ($P_0 = 10\%$, Target RR = 40%)
Drug is not promising if Stage 1 responder number \leq	5	2	1
Sample size for Stage 1	15	13	9
Drug is not promising if total responder number \leq	16	7	4
Sample size total	40	29	20

Under Amendment 6, enrollment of the NSCLC, SCCHN, and TCC of the GU tract cohorts will be completed as expansion cohorts at the 300 mg BID dose level. The sample size for each cohort will be increased to account for the heterogeneity of PD-1 pathway–treated and PD-1 pathway–naive subjects within the selected tumor types. The approximate number of subjects per tumor type is listed in Table 34, and the number of PD-1 pathway–treated subjects in each cohort will be limited to 10 in order to reduce the risk of any cohort having a significant imbalance between PD-1 pathway–treated and PD-1 pathway–naive subjects, thereby preserving the predicted levels of baseline efficacy observed with PD-1 pathway monotherapy. Subjects enrolled at the 100 mg BID will be analyzed independently. The sample size for each cohort expansion is based on a power of 90% to detect a target ORR of about 20% increase with a 1-sided alpha of 10% and 10% lost to follow-up.

Table 34: Sample Size Details (NSCLC, SCCHN, and TCC of the GU Tract)

Tumor Type	ORR		Sample Size
	H_0	H_a	
NSCLC	10%	30%	28
SCCHN	10%	30%	28
TCC of the GU Tract	10%	30%	28

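### The SAP groups Phase 2 subjects by tumor type alone, so 100 mg and 300 mg BID subjects share one primary ORR group, although the Protocol says the 100 mg subjects are analyzed separately

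*SAP*

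**What the plan says.** **SAP.** Section 5.3.3 puts every Phase 2 enrollee in the Phase 2 ITT population, uses that population for all Phase 2 efficacy, and says: "Treatment groups for this population will be defined according to the tumor type at the time of enrollment on Day 1". Section 5.3.4 uses the same tumor-type rule for the Phase 2 safety population. Section 7.3.1 estimates ORR, the Phase 2 primary variable, by treatment group with exact 95% confidence intervals.

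Section 5.2 opens with a dose-based statement, "Subjects will be summarized overall and based on the dose regimen initially assigned". Its Phase 2 list, however, has one row per tumor type, each at one unspecified dose of INCB024360 (epacadostat), for example "selected MTD/PAD of INCB024360 (Phase 2: NSCLC") and "selected MTD/PAD of INCB024360 (Phase 2: SCCHN"). The Phase 2 efficacy shells in Appendix C have cancer-type columns only. For Phase 1 the rule is different. Section 5.3.1 says: "Treatment groups for this population will be defined according to the treatment assignment at the time of enrollment on Day 1".

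**Protocol (Amendment 7).** Section 4.1.2 allows more than one PAD in Phase 2, and its Table 6 lists subjects at 100 mg and at 300 mg BID. It then says: "Subjects enrolled at the 100 mg BID dose level will be analyzed independently". Section 9.2.2 repeats this: "Subjects enrolled at the 100 mg BID will be analyzed independently". The 28 subjects per cohort are planned at 300 mg BID: "The sample size for each cohort expansion is based on a power of 90% to detect a target ORR of about 20% increase", from 10% to 30% in Table 34.

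**Versions.** The SAP is dated 26 NOV 2014 and was written for Protocol Amendment 1. Its Section 2.1 keeps it in force for later Protocol amendments unless it is itself amended, and its Table 15 lists only the original.

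**The concern.** ORR with its confidence interval is the main Phase 2 result, and the two documents disagree on who is in the denominator. An analyst following the SAP would report one NSCLC figure mixing two doses; an analyst following the Protocol would report the 300 mg cohort and set the 100 mg subjects apart. The same data can then give different ORRs and intervals, and the mixed figure describes neither dose. In an open-label study, leaving that choice open also allows it to be made after responses are known. The safety grouping in SAP Section 5.3.4 would likewise merge adverse event rates from two doses.

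**Working it through.** **1. Are the 100 mg subjects in Phase 2?** Yes; the Protocol's total is reached only if they are counted.
- Expansion cohorts (Protocol Table 6): 8 + 7 + 4 = 19 at 100 mg and 3 × 28 = 84 at 300 mg, together 103.
- Simon cohorts (Protocol Table 5): Stage 1 only, 15 + 13 + 9 = 37; both stages, 40 + 29 + 20 = 89.
- 103 + 37 = 140 and 103 + 89 = 192, which is the stated range of 140 to 192.

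The 19 subjects therefore fall within SAP Section 5.3.3.

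**2. The Protocol's 28.** With p0 = 10%, p1 = 30%, 1-sided alpha 10% and power 90%, the smallest exact binomial design is n = 25, with success at 5 or more responders (alpha 0.098, power 0.910). Allowing for 10% loss, 25/0.9 = 27.8, rounded up to 28. The figure reproduces, and Table 6 assigns it to 300 mg alone.

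**3. Denominators under the two rules**

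| Tumor | 100 mg | 300 mg | SAP group | 100 mg share |
|---|---|---|---|---|
| NSCLC | 8 | 28 | 36 | 22.2% |
| SCCHN | 7 | 28 | 35 | 20.0% |
| TCC | 4 | 28 | 32 | 12.5% |

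The SAP has no TCC row, so TCC is reached only through the general wording of Section 5.3.3.

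**4. Effect on the estimate.** Pooled ORR = (n100 × p100 + 28 × p300)/(n100 + 28). Assume p300 = 30%; p100 is not in the documents and is varied.

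| p100 | 0% | 10% | 20% | 30% |
|---|---|---|---|---|
| NSCLC | 23.3% | 25.6% | 27.8% | 30.0% |
| SCCHN | 24.0% | 26.0% | 28.0% | 30.0% |
| TCC | 26.3% | 27.5% | 28.8% | 30.0% |

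**5. Effect on the 95% interval (Clopper-Pearson).** Suppose 7 responders at 300 mg and none at 100 mg.
- 300 mg alone: 7/28 = 25.0% (10.7 to 44.9)
- NSCLC pooled: 7/36 = 19.4% (8.2 to 36.0)
- SCCHN pooled: 7/35 = 20.0% (8.4 to 36.9)
- TCC pooled: 7/32 = 21.9% (9.3 to 40.0)

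The first interval excludes the 10% reference rate; the other three do not.

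**6. Direction.** The lower limit exceeds 10% from 7 responders of 28, and from 8 of 32, 35 or 36. At a true 300 mg ORR of 30%, the chance of this is 78.0% with the 28 alone. For the pooled groups (sum of two independent binomials):

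| p100 | 0% | 10% | 20% | 30% |
|---|---|---|---|---|
| NSCLC | 63.5% | 74.0% | 82.4% | 88.8% |
| SCCHN | 63.5% | 72.8% | 80.6% | 86.7% |
| TCC | 63.5% | 69.1% | 74.2% | 78.8% |

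Pooling can therefore lower or raise the chance of a favorable reading.

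**The case against.** The strongest reply is that this is a version gap. The SAP was written when Phase 2 was to have one dose; more than one PAD came in with Protocol Amendment 4. The Protocol states the separate analysis plainly, a later SAP may exist, and SAP Section 5.2 itself begins with the assigned dose regimen. This is a fair account of the cause. It does not remove the conflict: the SAP declares itself in force for later Protocol amendments, and its Phase 2 list, both population definitions and the shells use tumor type alone. Protocol Section 9.4.1 also estimates ORR by treatment group without saying whether dose defines the group.

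Second, the 95% comparison with 10% is not a success rule: both documents say no formal efficacy hypothesis is tested. At the design's 1-sided 10% level, none of the examples in step 5 changes. The exact p-values are 0.018 (7/28), 0.063 (7/36), 0.055 (7/35) and 0.036 (7/32). With no 100 mg responder, the thresholds at that level are 6 of 28, 7 of 36, 7 of 35 and 6 of 32, so NSCLC and SCCHN change only at exactly 6 responders and TCC not at all. This stands, and step 5 should be read only as a description of the interval the plan will report. No 100 mg response is also the extreme case; at 20% the ORR shift is 2.2, 2.0 and 1.3 points.

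Third, a single 100 mg group across tumors could also count as separate analysis. That is possible, but it would still require a change to the SAP.

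**Conclusion.** The concern holds. As written, the SAP gives a primary ORR group of 36 (NSCLC), 35 (SCCHN) and, by its general wording, 32 (TCC), where the Protocol plans 28 at 300 mg and a separate analysis of the rest. The difference in denominators is certain. Its effect on the result is not: with 30% assumed at 300 mg and 0 to 30% at 100 mg, the pooled ORR is lower by 0 to 6.7 points in NSCLC (30.0 − 23.3), 0 to 6.0 in SCCHN (30.0 − 24.0) and 0 to about 3.7 in TCC (30.0 − 26.3). A 100 mg rate above 30% would move it upward. Because this determines the reported primary estimate, it should be corrected before database lock, unless a later SAP has already done so.

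Other outdated SAP content is secondary. Its Tables 2 and 4 keep NSCLC and SCCHN as Simon designs (17% against 40%, n = 38). It retains a Phase 2 pancreatic cohort and an optional top-up of PD-L1-positive subjects that the current Protocol lacks. It has no TNBC, gastric/GE junction or TCC group.

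**What to change.** Unless a later SAP already does this, amend the SAP before database lock.

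1. In Sections 5.2, 5.3.3 and 5.3.4 and in the Phase 2 shells, define groups as tumor type by assigned epacadostat dose. Report the NSCLC, SCCHN and TCC expansion-cohort ORR from the 300 mg subjects, and tabulate the 100 mg subjects separately.
2. Bring SAP Tables 2 and 4 and the Section 5.2 list into line with Protocol Tables 5, 6, 33 and 34, and remove the Phase 2 pancreatic cohort and the PD-L1-positive top-up.

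The cost is an SAP amendment and revised shells; no patients and no new data are needed. The drawback is that the 100 mg groups hold only 4 to 8 subjects each, so their intervals will be wide.
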